### **Full Board Review Risk Assessment**

Is this study more than minimal risk? (If NO, then this study should be submitted as an expedited protocol)

Yes

Does the study involve intervention and/or manipulation of the subjects or the subjects' environment (e.g., educational intervention or training, experimental or quasi-experimental design)?

Yes

Is the research categorized as interventional medical research?

Yes

Will monitoring for harms occur?

Yes

Describe monitoring for harm.

Please see the Data Safety Monitoring Plan under Notes and Attachments

Is there a Data and Safety Monitoring Plan (DSMP) for this study?

Yes

Is there a Data and Safety Monitoring Board (DSMB) for this study?

Yes

Is the DSMB independent?

No

Who will monitor the data?

The research team and [name], who is outside the department but serving on the DSMB.

What data will be monitored?

Adverse reaction to dexamethasone.

How frequently will data be monitored?

The board will meet after the first five subjects have had surgery. If no unexpected harms have been found, the board will meet every 3 months. Should an unexpected AE occur during the study, the board will be notified immediately and a decision will be made regarding continuing or discontinuing the study.

Describe how information relevant to the protection of participants will be managed addressing unanticipated problems involving risk to participants or others, interim results, and protocol modifications.

Should an unexpected AE occur during the study that is related to the research, the board will be notified immediately and a decision will be made regarding continuing or discontinuing the study.

Describe how the monitoring of data may ensure the safety of participants (e.g., a drastic blood pressure increase).  
**Dexamethasone may increase blood sugar in subjects with diabetes. All subjects with diabetes are carefully monitored for any rise in blood sugar per standard of care.**

List all the standard medical, behavioral, and/or educational procedures that will be utilized.  

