1. Potential subjects will see Drs. [name], [name], [name], [name] or [name] at their visit prior to elective anterior cervical spine surgery at the Spine or Neurosurgery Clinic. 2. Subjects will be told about the study at this visit, all questions will be answered by the surgeons and the research coordinator, all surveys that need to be completed will be shown to the potential subjects and they will be given the opportunity to consent. 3. If consented, the subject will be asked to complete baseline surveys (Bazaz, EAT-10, and Dysphagia Short Questionnaire) at this visit. The subject will also complete Standard of Care Patient Reported Outcome Measures (PROMS) at this visit. 4. The subject will be randomized to receive either single dose steroid (dexamethasone) or saline (placebo) prior to surgery. The dose is calculated based on body weight group will receive 0.3 mg/kg of intravenous dexamethasone (experimental group) 0.3 mg/kg saline (control group). The subject will not be charged for dexamethasone or saline. 5. The subject will undergo anterior cervical spine surgery per standard of care. 6. After administration of the antibiotics in the operating room, the single dose of steroid or saline will be given by the anesthesia team, who are blinded to the group assignment, via an intravenous bag (study drug) prepared by the investigational pharmacist, the only person who knows the group assignment. 7. The surgeon, patient, and research team are blinded to the group assignment. 8. The subject will be administered the surveys by phone call or in the hospital by the research coordinator on Day 1. 9. On Day 2, if the subject is still hospitalized, surveys will be administered by the research coordinator in the hospital or via phone call. 10. Following Day one surveys, and if the subject has been discharged, the subject will be called to complete the answers to the surveys via phone call at Day 2, Week 1, Week 2, Month 1, Month 3, Month 6 and Month 12. At Month 12, the subject will be asked to also complete standard of care PROMS. If the subject is in the clinic for follow up at the designated time frame for survey administration, the surveys will be completed in the clinic. If the subject is not in clinic at Month 12, the PROMS will be completed via phone call. 10. At the end of the study, all subjects will be called or mailed a letter indicating the group assignment they had been in. 11. Study Results will not be shared with the subjects.

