**Randomization to steroid or placebo; completion of Bazaz and the Short Dysphagia Questionnaire.**

What decision rules (e.g., stopping rules) will be considered?

**The board will meet after the first five subjects have had surgery. If no unexpected harms have been found, the board will meet every 3 months. Should an unexpected AE occur during the study, the board will be notified immediately and a decision will be made regarding continuing or discontinuing the study.**

Will the protocol be stopped once harms are proven to outweigh benefits?

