**Yes**

Describe how and where researchers will interact with participants, explaining how these interactions will be kept private.

**Researchers will interact with participants in private rooms of the spine clinic and neurosurgery clinic at the participant's history and physical visit prior to elective anterior spine surgery. They will see participants in their hospital room Day 1 after surgery and possibly Day 2 if the participant remains in the hospital past day 1. They will ask participants to complete the Bazaz, EAT-10, and Dysphagia Short Questionnaire on Day 1 and Day 2. They will call participants from a private room to complete questionnaires should the subject not return for regularly scheduled follow up visits. They will interact with participants at their standard of care follow up visits in the clinic.**

Describe any possibilities for risk or harm to the subjects as a result of their participation in the research (e.g., discomforts or hazards to the subjects). Please assess the severity of these risks.

**The only inconvenience is answering questions on the surveys face to face or via a phone call. The subjects will have a full understanding of the time frames by which they will be contacted to answer questions before consenting. Subjects will not be recruited if they don't want to answer the survey questions during the time frames. There should be no discomfort with administration of the study drug.**

Will subjects intentionally be deceived as to the purpose of the study?

**No**

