### **Potential Benefits**

Is there any known benefit to the individual subject as a result of participating in the research? Payments to subjects should not be included in this section, but addressed in the Payments/Reimbursements section.

Potential benefit is less difficulty swallowing if the subject is assigned to the steroid group.

Describe the potential benefit(s) to society and/or scientific / medical knowledge of the planned work.

The results of this study will provide evidence for the use of steroids as a treatment for reducing the incidence and severity of dysphagia among patients undergoing anterior cervical spine surgery. A recently performed study at our institution has promising results from a three-dose regimen of steroids.

Similarly, two recent clinical studies have also shown decreased dysphagia with a multi-dose steroid regimen. If the hypothesis of this proposal is supported, the use of a single dose of perioperative steroid specifically lends itself well to application in patients undergoing these procedures in outpatient surgery centers, improving the safety of such procedures.

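### Monitored safety data are defined by attribution to dexamethasone and no summary of harms by arm is planned, while the board trigger and the risk statements each conflict internally

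*Combined protocol and SAP*

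**What the plan says.** All references are to the combined protocol and SAP.

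- **Data monitored.** In the Full Board Review Risk Assessment, the full answer on which data will be monitored is "Adverse reaction to dexamethasone".
- **Who monitors.** The same section names the research team and one person "who is outside the department but serving on the DSMB". It states that the board is not independent.
- **Who is blinded.** The Design section's procedures say "The surgeon, patient, and research team are blinded to the group assignment". The infusion is "prepared by the investigational pharmacist, the only person who knows the group assignment".
- **Board trigger.** The answer on decision rules reads "Should an unexpected AE occur during the study, the board will be notified immediately", and the answer on monitoring frequency uses the same words. The answer on unanticipated problems adds a condition: "Should an unexpected AE occur during the study that is related to the research".
- **Drug harm.** The Risk Assessment rates the study above minimal risk. It says dexamethasone can raise blood sugar in subjects with diabetes, who are monitored for this in routine care. Its later answer on risk or harm to subjects says "The only inconvenience is answering questions on the surveys face to face or via a phone call", adds that giving the study drug should cause no discomfort, and names no drug harm.
- **Analysis.** The analysis answer in Design lists Mann-Whitney comparisons of dysphagia scores, a discrete-time survival model, an ordinal repeated-measures model and a comparison with the earlier three-dose study. It mentions no adverse events.
- **Stopping.** The Risk Assessment answers yes to stopping once harm is shown to exceed benefit.
- **Elsewhere.** For its description of harm monitoring, the form points to a Data Safety Monitoring Plan held as an attachment.

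**The concern.** A randomised placebo arm lets a trial separate the effects of a drug from the ordinary complications of surgery without anyone having to judge cause. That works best when every event is recorded in both arms and then counted by arm. Here the monitored data are defined by cause, and the people monitoring do not know who received the drug. An unfamiliar drug effect, or one that resembles a surgical complication, may never be classed as a drug reaction.

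The plan commits to a decision that weighs harm against benefit, but the supplied text describes no summary of harms by arm to support it. The two wordings of the board trigger would send different events to the board. A reader of the risk answer alone would not learn of the one drug harm that the same form names.

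**Working it through.** **1. Which events each stated route captures**

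| Route | Condition for an event to enter | Summarised by arm? |
|---|---|---|
| Monitored data | Seen as a reaction to dexamethasone | Not stated |
| Board notification, frequency and decision-rule answers | Unexpected | Not stated |
| Board notification, unanticipated-problems answer | Unexpected and related to the research | Not stated |
| Glucose monitoring | Subject has diabetes (routine care) | Not stated |

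An event that is expected after surgery, is not seen as a drug reaction and is not a glucose rise enters by none of these routes. Dexamethasone could make such an event more frequent, and only a count by arm would show it. An unexpected event judged unrelated to the research reaches the board under one wording of the trigger and not under the other.

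**2. What filtering by cause does to a comparison**

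Let p1 and p0 be the true risks of an event in the steroid and placebo arms, and let s be the share of such events recognised as suspected drug reactions. Assume s is equal in both arms, which is plausible while the assessors stay blinded.

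- Recorded risks: s × p1 and s × p0.
- Recorded difference: s × (p1 − p0).

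The denominator is still the patients randomised to each arm, and the comparison survives. The counts and the risk difference shrink by the factor s. The documents give neither s nor any event rate, so the loss cannot be quantified.

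**3. What the sample size allows even with complete recording**

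The plan has no safety figure to reproduce. Its sample size does reproduce: 2 × 32 = 64, and 64 / (1 − 0.20) = 80. With equal allocation (assumed) that is 40 per arm.

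- Zero events in 40, one-sided 95% upper limit: 1 − 0.05^(1/40) = 0.072, or 7.2%.
- Zero events in the first five operated patients, when the board first meets: 1 − 0.05^(1/5) = 0.451, or 45%. These five are not separated by arm, so this says little about the drug.
- Chance of at least one event in an arm of 40, 1 − (1 − p)^40, at assumed true rates: 33% for p = 1%, 55% for 2%, 87% for 5%.
- Power at two-sided 0.05 with 40 per arm, at assumed rates: about 32% for 5% v 15% (18% by Fisher's exact test), and about 53% for 5% v 20% (41% by Fisher).

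These figures show what 80 patients can exclude. They do not measure the effect of filtering by cause and would be the same after the fix. A table by arm would therefore be descriptive.

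**4. Added contacts**

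Design lists Day 1, Day 2, Weeks 1 and 2, and Months 1, 3, 6 and 12, which is eight postoperative contacts. 8 × 80 = 640 enquiries at most.

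**The case against.** The strongest reply is that the form defers to a Data Safety Monitoring Plan that is not in the supplied text. That plan may define event collection, assessment of cause and review by arm. This stands, and it makes the points on collection and on the missing table conditional. It does not remove the two triggers or the conflicting risk answers, which are in the form itself.

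A reader might also infer stronger conclusions that the documents do not support:

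- **That only drug-attributed events count.** Unexpected events also go to the board, and glucose is watched in subjects with diabetes. The form asks what is monitored. It does not say that other events go unrecorded.
- **That a blinded team is known to judge cause.** No one is named for this. It is an inference from who monitors and who is blinded.
- **That the event count has no denominator, or that the placebo comparison is thrown away.** The denominator is the patients randomised. Judgement made without knowledge of the arm is not biased by that knowledge, so suspected reactions could still be compared.
- **That harm cannot be weighed at all.** The text supports only that no comparative basis is stated.
- **That the plan claims a drug-safety gain.** The phrase "improving the safety of such procedures" is conditional on the hypothesis being supported and concerns later use in outpatient centres.
- **That subjects are not told of drug risks.** The consent pages were removed, so nothing follows about their content.

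**Conclusion.** The point holds in limited form. In the supplied text, monitored safety data are selected by presumed cause, the monitoring team is blinded, and no summary of harms by arm is planned. The stopping commitment therefore has no stated comparative basis. Followed as written, this would give poorer harm data than recording events regardless of cause.

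The loss has no calculable size. The 7.2% and 45% limits describe the sample size and not this defect. The conclusion assumes that the unseen Data Safety Monitoring Plan does not already require full recording and a summary by arm, and that the monitoring team would be the ones to recognise drug reactions.

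The two wordings of the board trigger and the two statements on drug risk are plain inconsistencies and depend on neither assumption. The whole is a cheap improvement that should be made. It does not undermine the efficacy comparison.

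**What to change.** Unless the Data Safety Monitoring Plan already does this (in which case the protocol should say so at these places):

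1. In the Full Board Review Risk Assessment, change the answer on monitored data to all adverse events in both arms, whatever the judged cause, asked with one open question at the scheduled survey contacts. A judgement of cause can still be recorded, but not as a condition for entry.
2. In the analysis answer under Design, add a table of events by randomised arm with risk differences and exact 95% confidence intervals. Label it descriptive and not a powered test. Include routine-care glucose values where available, since the form does not say they are captured as research data.
3. State whether the board sees events by arm during the trial and, if so, who supplies them, because only the pharmacist holds the allocation.

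In either case, reconcile the two wordings of the board trigger, and make the answer on risk to subjects consistent with the answers that rate the study above minimal risk and name raised blood sugar.

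The cost is one question at up to eight contacts for 80 patients (at most 640 enquiries), coding of the events reported, one table and some rewording. No visit, dose or efficacy analysis changes.

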**The surgeries are standard of care as well as completion of patient reported outcomes at the time frames listed.**

List the investigational interventions that will be utilized, above and beyond the standard of care.  
**Randomization to steroid or placebo; completion of Bazaz and the Short Dysphagia Questionnaire.**

What decision rules (e.g., stopping rules) will be considered?

**The board will meet after the first five subjects have had surgery. If no unexpected harms have been found, the board will meet every 3 months. Should an unexpected AE occur during the study, the board will be notified immediately and a decision will be made regarding continuing or discontinuing the study.**

Will the protocol be stopped once harms are proven to outweigh benefits?

**Yes**

Will clinical findings be shared with the subjects?

**Yes**

Describe how findings will be shared with the subjects.

**At the completion of the study all patients will be notified by phone call or letter their group assignment and results of the study.**

Will incidental findings be shared with the subjects?

**Yes**

Will WVU's procedures on incidental findings be followed?

**Yes**

Describe how and where researchers will interact with participants, explaining how these interactions will be kept private.

**Researchers will interact with participants in private rooms of the spine clinic and neurosurgery clinic at the participant's history and physical visit prior to elective anterior spine surgery. They will see participants in their hospital room Day 1 after surgery and possibly Day 2 if the participant remains in the hospital past day 1. They will ask participants to complete the Bazaz, EAT-10, and Dysphagia Short Questionnaire on Day 1 and Day 2. They will call participants from a private room to complete questionnaires should the subject not return for regularly scheduled follow up visits. They will interact with participants at their standard of care follow up visits in the clinic.**

Describe any possibilities for risk or harm to the subjects as a result of their participation in the research (e.g., discomforts or hazards to the subjects). Please assess the severity of these risks.

**The only inconvenience is answering questions on the surveys face to face or via a phone call. The subjects will have a full understanding of the time frames by which they will be contacted to answer questions before consenting. Subjects will not be recruited if they don't want to answer the survey questions during the time frames. There should be no discomfort with administration of the study drug.**

Will subjects intentionally be deceived as to the purpose of the study?

**No**

## **HIPAA**

Does the research involve protected health information (PHI)?

**Yes**

Will the HIPAA and consent forms be combined? If not, attach a separate HIPAA Authorization to the Notes & Attachments page.

**Yes**

Are you requesting a HIPAA waiver? If yes, attach a HIPAA Waiver Form on the Notes & Attachments page.

**No**

Will the research being conducted at a covered entity require authorization from the subject? If yes, attach a HIPAA Form on the Notes & Attachments page - only if a combined consent with HIPAA is not used.

**No**

Are you transferring identifiable data to or from another institution? If yes, attach a signed and WVU Legal Counsel approved HIPAA Data Use Agreement Form on the Notes & Attachments page.

**No**

Will the research being conducted at a covered entity involve data that is de-identified? If yes, attach a HIPAA De-Identification Certification Form on the Notes & Attachments page. You can find the form [here](#) (this is only for NHR studies).

**No**

Will the study include deceased individuals? If yes, attach a HIPAA Decedents Form on the Notes & Attachments page.

**No**

Will data/samples with identifiers be received from another entity? If yes, attach a signed, Legal Counsel approved HIPAA Data Use Agreement Form on the Notes & Attachments page.

No

### Subjects

Indicate the maximum number of subjects to be enrolled or medical records to be reviewed at all sites by the WVU or VAMC research team.

80

Provide a rationale for choosing your sample size.

Scores from the Bazaz scale, the EAT-10, and the Dysphagia Short Questionnaire from the two groups will be compared at the various time points using the Mann-Whitney U test. Statistical significance is set at  $p<0.05$ . With a power of 0.80 and a clinical meaningful difference of 30% in scores, an estimated 32 patients per group is needed. However, based on a recent unpublished study at our institution, we expect a dropout rate of approximately 20%, and therefore plan for a total sample size for this study of 80 patients.

State the requirement(s) to become a participant in the study (e.g., age range, sex, language spoken, class enrollment/ranking).

Ages 18-80; undergoing elective ACDF, hybrid constructs, corpectomies, disc arthroplasty surgery

Explain why selection of participants will be equitable addressing gender, ethnicity, and/or race of subjects.

No one will be excluded based on gender, ethnicity or race. Exclusion criteria include: < 18 years of age; major trauma or neoplastic or infectious conditions requiring surgery. Also excluded will be patients undergoing anterior-posterior operations, those with a history of previous anterior cervical spine surgery, any patient requiring a halo vest, patients on chronic steroids, and patients remaining intubated post-operatively, and women who are pregnant.

In outline format and chronological order, describe what will be done to identify and recruit participants (e.g., A, B, C or 1, 2, 3).

1. Potential subjects will see Drs. [name], [name], [name], [name] or [name] at their History and Physical visit prior to elective anterior cervical spine surgery at the Spine Center. 2. Subjects will be told about the study at this visit, all questions will be answered by the surgeons and the research coordinator, all surveys that need to be completed will be shown to the potential subjects and they will be given the opportunity to consent. 3. If consented, the subject will be asked to complete baseline surveys (Bazaz, EAT-10 and Dysphagia Short Questionnaire) at this visit. 4. The subject will be randomized to receive either single dose steroid (dexamethasone) or saline (placebo) prior to surgery.

Will any of the subjects be less than 18 years old?

No

Will your study target populations such as pregnant women, fetuses, neonates, or any groups likely to be vulnerable to coercion or undue influence such as children, prisoners, individuals with impaired decision-making capability or economically or educationally disadvantaged persons?

No

Does this research involve participants who could be coerced or unduly influenced, such as current students/employees of research team members?

No

Does the protocol deal with cancer prevention, treatment, or diagnosis (including surveys)?

No

Has this protocol been reviewed by Clinical Trials Working Group (CTWG)? If yes, please attach the CTWG's correspondence on the Notes & Attachments page.

No

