Swallowing symptoms will be measured using the patient reported Bazaz Dysphagia Scale, EAT-10 survey, and the Dysphagia Short Questionnaire. Swallowing data will be obtained pre-operatively, one and two days post-operatively and then one week, two weeks, four weeks, three months, six months, and one year post-operatively. Scores from the Bazaz Dysphagia Scale and the Dysphagia Short Questionnaire from the two groups will be compared at the various time points using the Mann-Whitney U test. Power and sample size calculations are based on the presence or absence of dysphagia at two weeks. Based on a literature review, we postulated that 50% of the patients in the control group would experience mild, moderate, or severe dysphagia. If that figure can be improved to the point where just 20% of the patients are similarly affected then that, in our opinion, would represent clinical success. Under the above scenario, 32 patients in each group would give us 81% power to reject the null hypothesis. Assuming a dropout rate of 20% our total sample size for the study is 80. Statistical significance is set at  $p < 0.05$ . We plan to analyze the data in three ways. First, we will look at the time-to-event where the event is "no dysphagia" in a discrete time survival model. Second, we will use a repeated measures ordinal categorical model to assess the effect of steroid/control in a generalized linear model. Lastly, we will compare the data from this study with that of our previous three-dose model to assess any difference in the degree of impact of the two dosing regimens.

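### The two sample-size rationales rest 32 per group on incompatible bases, and the stated 80–81% power on 50% vs 20% dysphagia is met only by an undeclared one-sided test

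*Combined protocol and SAP*

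**What the plan says.** The plan gives two justifications for one number.

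- **Design section, answer on the method of analysis.** The basis is binary, at a single visit: "Power and sample size calculations are based on the presence or absence of dysphagia at two weeks". For the control rate, "we postulated that 50% of the patients in the control group would experience mild, moderate, or severe dysphagia". The target is worded as "If that figure can be improved to the point where just 20% of the patients are similarly affected". The result is that "32 patients in each group would give us 81% power to reject the null hypothesis".
- **Subjects section, rationale for sample size.** Here the outcome is a score on each of three instruments (Dysphagia Short Questionnaire, EAT-10, Bazaz). The planned test is described thus: "from the two groups will be compared at the various time points using the Mann-Whitney U test". The power claim follows: "With a power of 0.80 and a clinical meaningful difference of 30% in scores, an estimated 32 patients per group is needed".

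Both sections set significance at p < 0.05, and neither says whether the test is one- or two-sided. Both add 20% dropout and arrive at 80 patients in total.

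**The concern.** The endpoint changes from one binary outcome at two weeks to scores on three instruments at several visits. The 30% changes from an absolute difference in proportions (50% minus 20%) to an unexplained difference in scores. The second version has no variability behind it, so its power claim has nothing to be calculated from. The first version has all its inputs except sidedness, and with a conventional two-sided test they do not give 81%.

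The sample-size rationale is what readers use to interpret a null result. As written, the Subjects section invites them to treat a non-significant Mann-Whitney comparison on any of the three scales as adequately powered. The Design section invites them to assume a chance of about one in five of missing the target effect. With a two-sided test that chance is nearer 27–28%.

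**Working it through.** **Inputs.** From the Design section: control rate 0.50, treated rate 0.20, 32 per group, 81% power. From the Subjects section: 32 per group, 0.80 power, 30% in scores, Mann-Whitney. From both: p < 0.05, 20% dropout, total 80. Equal allocation is implied by the equal group sizes.

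**1. Reproducing the stated figure (50% vs 20%).** The pooled rate is (0.50 + 0.20)/2 = 0.35. Power = Φ{[Δ√n − z·√(2·0.35·0.65)] / √(0.50·0.50 + 0.20·0.80)}, with Δ = 0.30 and n = 32. Here Δ√n = 1.697, √0.455 = 0.6745 and √0.41 = 0.6403.

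- One-sided 5%, z = 1.645: (1.697 − 1.110)/0.6403 = 0.918, so power is **82.1%**. The smallest n for 81% is (1.110 + 0.878·0.6403)²/0.09 = 31.05, rounded up to 32. This matches the plan.
- Two-sided 5%, z = 1.960: (1.697 − 1.322)/0.6403 = 0.586, so power is **72.1%**. The n for 80% is (1.322 + 0.8416·0.6403)²/0.09 = 38.5, rounded up to 39.

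| Method, 32 per group | Two-sided | One-sided |
|---|---|---|
| Normal, pooled | 72.1% | 82.1% |
| Arcsine | 73.0% | 82.4% |
| Normal, unpooled | 75.5% | 84.3% |
| Pearson chi-square, exact enumeration | 73.4% | 82.1% |
| Fisher's exact test | 64.4% | 74.8% |

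No two-sided method in the table reaches 80%.

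**2. If nobody is lost.** With 40 per group, two-sided power is 81.6% (normal), 81.7% (exact Pearson) or 74.9% (Fisher). The plan claims 81% for 32 per group, not for 40.

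**3. Dropout.** 64/(1 − 0.20) = 80, which is correct.

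**4. What a score comparison would need.** For 80% two-sided power with 32 per group, the standardised difference is (1.960 + 0.842)·√(2/32) = 0.70. Allowing for Mann-Whitney efficiency 3/π, it is 0.70/√0.955 = 0.72. A 30% relative fall in the mean reaches this only if SD/mean is at most 0.30/0.72, about 0.42. The plan gives no SD.

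**5. Applying the two-week assumption to scores.** Suppose half of controls are at none and none is scored 0. Let m be the mean among the affected. Then E[X] = 0.5m and E[X²] ≥ 0.5m² = 2·E[X]², so the SD is at least the mean. A 30% fall is then at most 0.30 control SD. At 0.30 SD, approximate Mann-Whitney power is Φ(0.30·√(32·0.955/2) − 1.960) = Φ(−0.787), about 22%.

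**6. Range under assumed Bazaz distributions.** These are simulations, two-sided, 32 per group, treated mean 30% lower, categories scored 0 to 3. All splits are assumptions.

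| Controls: none/mild/moderate/severe (%) | Power |
|---|---|
| 50/25/15/10, 50/35/10/5, 50/17/17/16, 50/50/0/0 | 18–25% |
| 20/40/30/10 | about 42% |
| 10/50/30/10 | about 58% |
| 5/15/60/20 | about 80–84% |

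The shape of the treated distribution also matters. With half of controls at none, one extreme treated shape (80% none, the rest moderate or severe) gave 46%.

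**The case against.** The strongest defence is that the Design section expressly names its basis, and the Subjects section repeats the same 32, 20% and 80. Its 30% may therefore be loose shorthand for the 30-point difference. That is plausible, but the words say scores and sit next to a rank test of three instruments, so a reader cannot be expected to make the translation.

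A second defence is that neither section says two-sided, so a one-sided test is open and delivers the figure. This stands in part. It is why the conclusion on power is conditional, but an undeclared one-sided test cannot be left to inference.

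Third, the full ordinal scale may carry more information than the binary cut. With 50% vs 20% affected, two-sided Mann-Whitney power was about 74–75% under proportional odds (odds ratio 4). It was 85–91% if every affected treated patient was only mild, depending on the assumed control split. So some score assumptions do reach 80%, but the plan states none of them.

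Two stronger readings are tempting. A reader might infer that 32 per group fails on every interpretation. The documents do not support that: a one-sided test of 50% vs 20% gives about 82%, and a 30% score reduction can reach about 80% when few controls are at none. A reader might also infer that the score tests have only about 20% power. That holds only if half of controls score zero. The plan postulates the 50% rate only for its two-week endpoint, while the score tests span visits from the first day after surgery. The plan gives no numeric scoring for any of the three scales.

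**Conclusion.** The contradiction is in the text and both rationales cannot stand. On the binary basis the stated power is wrong for a two-sided 0.05 test: about 72–73% with 32 per group (64% with Fisher's exact test) instead of 80–81%, a shortfall of roughly 8 points. It is right only for a one-sided 5% test, which is not declared. These figures rest solely on the plan's own 50%, 20% and 32.

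The score-based claim is unverifiable, not shown to be false. Its power depends on distributions that the plan does not give, and the assumed cases run from under 20% to over 80%. The 20% dropout adjustment is arithmetically correct.

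**What to change.** - In the Subjects section, delete the reference to a 30% difference in scores. Use the Design section's basis in both places: 50% vs 20% with any dysphagia (Bazaz mild or worse) at two weeks.
- Name the test and state whether it is one- or two-sided.
- If it is two-sided, restate power as about 72–73% with 32 evaluable per group (64% if Fisher's exact test is chosen). A figure of about 82% by chi-square may be quoted only for the case where all 40 per group have two-week data.
- If a one-sided test was intended, declare it. About 82% then applies to the chi-square test or its normal approximation.
- State that the Mann-Whitney score comparisons were not the basis for the sample size.

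The change is wording in two answers, at the price of a less favourable stated power if the test is two-sided. Keeping 80 patients and accepting that power is the sponsor's choice. For comparison, 80% two-sided power needs 39 evaluable per group by the pooled normal formula. That is 39/0.80 = 48.75, rounded up to 49 per group, or 98 in total.
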